6. SECONDARY ENDPOINTS

All the secondary analyses will be conducted on PP. Additional sensitivity analysis will be conducted on all subjects who were administered any test article excluding subjects who drop out prior to administering any test article. At least one observation should be recorded.

6.1. Definition

Binocular visual performance:

The following measurements will be used to assess the performance of the test and control products in a controlled laboratory setting which simulate a wide range of visual conditions encountered while driving.

1. High luminance (~500 lux) high contrast (90%) LogMAR distance visual acuity

- 2. High luminance (~500 lux) low contrast (10%) LogMAR distance visual acuity
- 3. Low luminance (~1 lux) high contrast (90%) LogMAR distance visual acuity
- 4. High luminance (~500 lux) contrast threshold (Pelli-Robson chart)
- 5. Low luminance (~1 lux) contrast threshold (Mesotest II instrument by Oculus, Germany)

The order of the vision tests will be randomized for each condition. The ETDRS logMAR chart will be used, which is scored on a letter by letter basis (-0.02 log units per letter correctly identified). A number of different EDTRS charts will be used to reduce potential learning effects. Letter contrast sensitivity will also be determined binocularly using the Pelli-Robson chart, scored on a letter by letter basis (0.05 log units per each letter correctly identified). The ETDRS logMAR chart and the Pelli-Robson contrast sensitivity chart are validated techniques routinely used in research to accurately quantify visual performance. Room illuminance will be controlled using dimmer switches and quantified using a lux meter.

There will be two secondary endpoints considered from binocular visual performance evaluation:

- Low luminance ~1 lux) high contrast (90%) distance visual acuity
- Low luminance (~1 lux) contrast threshold

During low luminance contrast threshold evaluation, five Landolt C targets in random orientation will be presented for each of the four contrast levels 95%, 80%, 63% and 50%. Participants will be asked to correctly identify the orientation of the Landolt C. The number of correct response will be recorded for each contrast level. This entire test will be done with and without the presence of a glare source.

Sign recognition (percentage)

Participants will be instructed to report the identity of a percentage of the standard road signs (typically about 42 signs dependent on the route travelled) containing about 65 items of information as they drive around the circuit. We will also measure the recognition distance using the in-vehicle measurement system for one specific road sign while the participant is driving.

Hazard avoidance:

Participants will be required to report and avoid hitting any of nine large, low contrast grey foam "hazards" (220 cm x 80 cm x 15 cm) positioned orthogonally in the driving lane along the roadway, the locations of which will be randomized between trials.

Pedestrian recognition distance:

The in-vehicle measurement system will be utilized to determine the distance at which the participant (as a driver) first recognizes the presence of two pedestrians positioned at the side of the road. An experimenter will act as the pedestrian and "walk in-place" at the end of a 400 m straight section of roadway which starts and finishes at approximately the same elevation, but features a dip halfway along its length. The pedestrian will not be surrounded by any visual clutter or lighting. To reduce expectancy effects, a series of four flashing LEDs and four retro-reflective bollards will be positioned around the circuit to increase the instances of flashing lights and retro-reflective material being presented to the driver. Figure 2 shows an example of a low contrast hazard (grey foam) in the driving lane in front of some retroreflective bollards and signage.

On each lap the pedestrian will walk in place as the test vehicle approaches, facing directly towards

the oncoming vehicle; this allows for the inclusion of naturalistic motion and ensures the safety of the pedestrian. The pedestrian will wear biomotion reflective strips on the moveable joints, which has been shown to be a configuration that allows good discrimination between different levels of spherical blur².

The main dependent variable is the driver's response distance to the pedestrian which is defined as the distance from the test vehicle to the pedestrian at that moment when the response button is pressed to indicate recognition of the presence of the pedestrian at the side of the road.

High luminance binocular visual performance:

This includes the following endpoints:

- 1. High luminance (~500 lux) high contrast (90%) logMAR distance visual acuity
- 2. High luminance (~500 lux) low contrast (10%) logMAR distance visual acuity
- 3. High luminance (~500 lux) contrast threshold (Pelli-Robson chart)

6.2. Secondary Analysis Methods

Binocular distance visual acuity (LogMAR)

Binocular low luminance high contrast distance visual acuity will be analyzed using a linear mixed model to test for the difference between Test and Control 1. Sequence of lens wear, period, lens type, first order carryover effect will be included in the model as fixed effects. An appropriate covariance structure will be chosen to model the residual errors between measurements within the same subject across periods. Covariance structures considered will be:

- Compound Symmetry (CS)
- Heterogeneous Compound Symmetry (CSH)
- Unstructured (UN)
- Ante-dependence (ANTE(1))

For ANTE(1) structure, subject will be included in the model as random effects. The covariance structure that returns the lowest AICC will be selected as the structure that best fit the data.

The null and alternative hypotheses for non-inferiority of Test lens relative to Control 1 are as follows:

$$H_0: \mu_T - \mu_C \ge 0.1 H_A: \mu_T - \mu_C < 0.1,$$

where $\mu_T - \mu_C$ is the mean difference between Test lens and Control 1 lens. Non-inferiority of the Test lens relative to the Control 1 lens will be concluded if the upper limit of the 95% confidence interval of the LSM difference between Test and Control 1 is less than 0.1.

Low luminance contrast threshold (%)

Low luminance contrast threshold will be analyzed using a generalized linear mixed model with a binomial distribution and the logit and the link function. Sequence, period, lens type, first order carry-over, contrast level and the interaction contrast level by lens type will be included as fixed effects and subject as random effect. An unstructured covariance matrix (UN) will be used to model the correlation between measurements from the same subject and period across contrast level. If convergence problems are encountered with the unstructured covariance matrix, a model with compound symmetry covariance matrix (CS) will be considered

The null and alternative hypotheses for no-difference between Test and Control 1 are as follows:

$$H_0: OR = 1 H_A: OR \neq 1,$$

where OR is the odds ratio of the number of correctly identified orientation of the Landolt C. No statistical difference between Test lens and Control 1 lens will be concluded if 1 falls within the 95% confidence interval of the LSM ratio, OR, of Test Over Control 1.

Sign Recognition and Hazard Avoidance (%)

Proportion of correctly identified sings and proportion of hazard avoidance will be analyzed separately using a generalized linear mixed model with beta distribution and logit link function. Each model will include sequence, period, lens type, first order carry-over, driving time (day or night), and the 2-way interactions: lens*time, sequence*time, period*time and carry*time as fixed effect factors. An unstructured covariance matrix (UN) will be used to model the correlation between measurements from the same subject across periods. If convergence problems are encountered with the unstructured covariance matrix, a model with compound symmetry covariance matrix (CS) will be considered. Non-significant interactions at the 15% significance level will be excluded from the model. The interaction between lens type and driving time will be forced into the final model.

The null and alternative hypotheses for no-difference between Test and Control 1 are as follows:

$$\begin{array}{l} H_0: OR = 1 \\ H_A: OR \neq 1, \end{array}$$

where OR is the odds ratio of hazard avoidance at night driving time of Test over Control 1. No statistical difference between Test and Control 1 will be concluded if 1 falls within the 95% confidence interval of the odds ratio.

Pedestrian Distance Recognition and Road Sign Recognition

Pedestrian distance recognition and road sign recognition distance (or log-transformed distance) will be analyzed separately using a linear mixed model; sequence of lens wear, period, lens type, first order carry-over, driving time (day or night), and the 2-way interactions: lens*time, sequence*time, period*time and carry*time will be included in the model as fixed effects. Age will be included as fixed covariate when appropriate. An appropriate covariance structure will be

selected to model the correlation between measurements across periods within the same subject and driving time. Covariance structures that will be considered include:

- Compound Symmetry (CS)
- Heterogeneous Compound Symmetry (CSH)
- Unstructured (UN)
- Ante-dependence (ANTE(1))

For ANTE(1) structure, subject and driving time nested within subject will be included in the model as random effects. For the remaining structures only subject will be included as random effect. The covariance structure that returns the lowest Akaike Information Criteria Corrected (AICC) will be selected as the structure that best fit the data¹². Heterogeneous residuals covariance structures (R-side) across driving time will be considered when appropriate. The log-likelihood ratio test will be used to test for the homogeneity between the residual covariance structures. The Kenward and Roger method will be used for the denominator degree of freedom. Non-significant interactions at the 15% significance level will be excluded from the model. The interaction between lens type and driving time will be forced into the final model.

Results from the final selected model will be reported as least-square mean (LSM) estimates with 95% confidence intervals.

The null and alternative hypotheses for non-inferiority of Test lens relative to Control 1 are as follows:

$$H_0: \mu_T - \mu_C = 0$$

$$H_A: \mu_T - \mu_C \neq 0,$$

where $\mu_T - \mu_C$ is the mean difference of distance recognition at night driving between Test and Control 1. No statistical difference between Test and Control 1 will be concluded if 0 falls within the 95% confidence interval of the LSM difference between Test and Control 1.

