1.3. Study Design

This is a randomized, single-masked, crossover, dispensing study, with 4 visits. Comparisons between the JJVC investigational lens and the two controls will occur at visit 2 (vision testing) and visit 3 and 4 (driving performance). Approximately 28 subjects will be screened and enrolled to ensure that at least 24 subjects complete the study.

The study begins with an initial visit (Visit 1 - Day 0). If a subject is found to meet all eligibility criteria, he/she will be randomized to the Test lens and one of the Control lenses for an initial lens fitting evaluation using a 2x2 crossover design (Test/Control1, Test/Control2, Control1/Test, Control2/Test); otherwise, the subject will be deemed ineligible for this study.

After the fitting evaluation at Visit 1, non-discontinued subjects will be scheduled for three additional visits. Visit 2 will occur approximately 24 hours after the initial visit, visit 3 will occur approximately 24 hours after visit 2 and visit 4 will occur approximately 1 week after visit 3. At Visit 2, eligible subjects will be randomized and laboratory testing will be conducted on all test articles in a random order based on the randomization scheme. Subjective assessment of driving performance in both daytime and nighttime will be performed in a random order, based on the

randomization scheme, in two different visits at Visit 3 and Visit 4. Unscheduled follow-up visits may occur during the study. The planned duration of lens wear is for the experimental procedures only (between 1-3 hours during visits 2-4). Participants will not have access to test articles at study closure.

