CLASS tseqpg2 aperiod trta carry1a subjid parcat6 sexn ; MODEL aval/n= age sexn tseqpg2 aperiod trta|parcat6 carry1a / S DIST=BINOMIAL LINK=LOGIT; RANDOM INTERCEPT / SUBJECT=subjid; RANDOM parcat6 / RESIDUAL SUBJECT=aperiod(subjid) TYPE= covariance_matrix; ESTIMATE "Test vs Control1" lens -1 0 1, *secondary analysis; "Test vs Control2" lens 0 -1 1 / CL ILINK EXP; *other analysis;

RUN;

Where ads: Analysis data set n: number of targets subjid: subject identification sexn: Gender tseqpg2: Lens wear sequence (6 levels) aperiod: Study Period (3 levels) trta: Study lens type (Test, Control1, Control2) parcat6: Contrast level (4 levels) carry1a: First order carryover effect covariance_matrix: Compound Symmetry (CS) and Unstructured (UN)

Sign Recognition and Hazard Avoidance

PROC GLIMMIX DATA= ads;

CLASS driveseq asper trta carry1a parcat5 sexn; MODEL aval= age sexn driveseq asper|parcat5 trta|parcat5 carry1a / DDFM=KR2 S DIST=BETA LINK=LOGIT; RANDOM INTERCEPT / SUBJECT=subjid; RANDOM asper / RESIDUAL SUBJECT= parcat5 (subjid) TYPE=covariance_matrix; **Secondary analysis; ESTIMATE "Night: Test vs Control1" trta -1 0 1 trta*parcat5 0 -1 0 0 0 1 / CL ILINK EXP; **Other Analysis; ESTIMATE "Day: Test vs Control1" trta -1 0 1 trta*parcat5 -1 0 0 0 1 0, "Day: Test vs Control2" trta 0 -1 1 trta*parcat5 0 0 -1 0 1 0, "Night: Test vs Control2" trta 0 -1 1 trta*parcat5 0 0 0 -1 0 1 / ADJUST=bonferroni CL ILINK EXP ;

RUN;

Where ads: Analysis dataset subjid: subject identification sexn: Gender driveseq: Lens wear sequence (6 levels) asper: Study Period (3 levels) trta: Study lens type (Test, Control1, Control2) parcat5: Driving time (day or night) carry1a: First order carryover effect covariance matrix: Compound Symmetry (CS) and Unstructured (UN)

Pedestrian Distance Recognition and Road Sign Recognition

PROC GLIMMIX DATA= ads;

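### The low-luminance contrast model has no rule for a Test or Control 1 cell at ceiling, where the averaged odds ratio is not estimable and the stated rule can read that as no difference

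*SAP*

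**What the plan says.** SAP 6.1 describes the test: "five Landolt C targets in random orientation will be presented for each of the four contrast levels 95%, 80%, 63% and 50" per cent. It is done with and without glare; hypothesis 2 (SAP 1.4.2) concerns the condition without glare, Test against Control 1.

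SAP 6.2 analyses the counts with a "generalized linear mixed model with a binomial distribution and the logit and the link function", with sequence, period, lens and first-order carry-over, and adds that "contrast level and the interaction contrast level by lens type will be included as fixed effects and subject as random effect". Appendix A matches: "MODEL aval/n= age sexn tseqpg2 aperiod trta|parcat6 carry1a", where `trta` is the lens and `parcat6` the contrast level.

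The tested quantity is a single least-squares-mean OR of Test over Control 1. In Appendix A it is one lens contrast with no interaction coefficients: "lens -1 0 1, *secondary analysis". The averaging over levels is not written in words; it follows from the least-squares-mean definition and from this contrast.

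If the unstructured covariance does not converge, "a model with compound symmetry covariance matrix (CS) will be considered". No other fallback is given. The rule that removes interactions not significant at 15% is stated for the driving models in SAP 5.2 and 6.2, not for this one. No statistical difference is concluded if the 95% interval contains 1.

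Protocol 14.6 planned a Poisson model for this endpoint, also with the interaction. The SAP amendment history records the change, and SAP 1.1 makes the SAP prevail.

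**The concern.** The model gives each lens its own logit at each contrast level. A logit is unbounded when every response is correct, and the tested OR weights the four levels equally, so one level without errors is enough to remove the information in the average, whatever the other three levels show. Under the protocol's Poisson model an all-correct cell has a mean of 5 and a finite logarithm, so the exposure came with the change to the logit.

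Ceiling is plausible without being established. The easiest level is 95% contrast, the condition is without glare, and subjects must have best-corrected acuity of 20/20 or better. On the other side, acuity of 20/20 is not a Mesotest score at about 1 lux.

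The decision rule favours an uninformative interval. At stake is a real loss of low-luminance contrast vision with the Test lens being reported as no difference on a named secondary hypothesis.

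**Working it through.** **Plan's own figure.** There is none to reproduce: the documents give no power, sample size or expected correct rate for this endpoint.

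**Cell size.** SAP 1.3: "Approximately 28 subjects will be screened and enrolled to ensure that at least 24 subjects complete the study". With 24 completers and 5 targets per level, each lens-by-level cell has 24 × 5 = 120 responses.

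**The tested quantity.** log OR = ¼ Σ (logit p_Test,l − logit p_Control1,l) over the levels l = 1 to 4. If one of these eight proportions is estimated as 1, its logit has no finite estimate and neither has the average. Control 2 does not enter the sum.

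**Chance of a ceiling cell.** Assume independent responses with the same rate p at one level for both lenses. One cell is all-correct with probability p^120; Test or Control 1 with probability 1 − (1 − p^120)².

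| Assumed p | p^120 | Test or Control 1 at ceiling |
|---|---|---|
| 0.95 | 0.2% | 0.4% |
| 0.97 | 2.6% | 5% |
| 0.98 | 8.9% | 17% |
| 0.99 | 30% | 51% |
| 0.995 | 55% | 80% |

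Variation between subjects at the same average rate raises the single-cell figure, because the mean of p^5 over subjects is at least the fifth power of the mean p.

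**What the fit does.** One illustrative dataset used the planned design (24 subjects, six sequences, three periods, carry-over; age and sex omitted). Control 1 was 120/120 and Test 101/120 at the 95% level, with Test also worse at the other three.
- Ordinary logistic fit with the interaction: standard error 4.5 at iteration 10, 55 at 15 and 2978 at 25, so the Wald interval runs from 0 to infinity.
- Mixed model by pseudo-likelihood, CS: no convergence. The standard error was 0.52 at step 5 (interval 0.04 to 0.31, which excludes 1), 6.2 at step 10 and 248 at step 16. With UN it grew more slowly, to 11.6 at step 16.
- Logistic fit without the interaction: OR 0.33 (0.23 to 0.49).
- Interaction kept, Firth penalisation: OR 0.19 (0.09 to 0.40).

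With only Control 2 all-correct, the Test-versus-Control 1 OR stayed finite: 0.37 (0.25 to 0.56) in the logistic fit. In the mixed model that contrast was also stable, although the iterations as a whole did not settle.

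**How often the conclusion is affected.** Logistic fits to the planned design, 400 runs, assumed Control 1 rates 0.99/0.97/0.92/0.85, true log OR −1.0:

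| Runs | Number | No difference, interaction kept | No difference, common OR |
|---|---|---|---|
| With a ceiling cell | 106 | 100% | 3% |
| Without | 294 | 19% | 2% |

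**Dependence on the assumed rates.** Simplified logistic simulation: Test and Control 1 only, 24 subjects, subject SD 0.5 logits, Test shifted by −0.7 at every level (OR = e^−0.7 ≈ 0.50).

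| Control 1 rates by level (approximate) | Detected, averaged OR | Detected, common OR |
|---|---|---|
| 0.99/0.97/0.86/0.60 | about 18% | about 94% |
| 0.97/0.92/0.82/0.60 | about 85% | about 98% |
| 0.95/0.90/0.80/0.60 | about 96% | about 99% |

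With an uneven loss (log ORs −1.5, −0.7, −0.3 and 0 from easiest to hardest; middle row's rates), the common OR detects about 60% and the averaged OR 85% to 90%.

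**The case against.** A reader might infer that any all-correct cell makes the interval infinite, so that no difference follows automatically. The documents do not support that. The cell must belong to Test or Control 1 and contain no errors across all subjects; one subject scoring 5 of 5 is not enough. The unbounded interval is the limit of an ordinary Wald fit. The planned mixed model fails to converge instead, an early stop can even exclude 1, and the SAP does not say what is concluded from a failed fit. Failure is also visible: SAP 11.2 requires review by a second statistician and SAP 11.3 requires changes to be documented and justified. That stands, but a remedy chosen after the data are seen is weaker than one stated now.

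Nor does a nearly full cell guarantee the result. In the 400-run simulation, runs without a ceiling cell missed the difference 19% of the time, not always.

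The size rests on rates that nobody has stated, and at lower rates the loss almost vanishes. That stands. So does the defence of the interaction: both documents pre-specify it, and it performs better when the loss is concentrated at the easiest level. Removing it in all cases is therefore not warranted.

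Finally, reading an interval that contains 1 as no difference is a wider feature of the no-difference secondary hypotheses. That is a separate matter, but here it turns a numerical failure into a possible favourable conclusion.

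**Conclusion.** The concern holds in conditional form. A Test or Control 1 cell with every response correct leaves the planned averaged OR without a usable estimate, the UN-to-CS step cannot restore one, and the decision rule would count an unbounded interval as no statistical difference. How likely this is depends on correct rates that the documents do not give: from about 0.4% to about 80% over assumed top-level rates of 0.95 to 0.995. The loss of power likewise ranges from severe to negligible. The detection rates come from logistic approximations without the planned residual covariance; the mixed-model behaviour was checked on illustrative datasets only. One of six secondary hypotheses is affected and the primary is not. It should be fixed, but it does not threaten the trial's main conclusion.

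**What to change.** In SAP 6.2 and Appendix A:

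1. Pre-specify that if any Test or Control 1 lens-by-level cell is at 0% or 100%, or the model does not converge under CS, hypothesis 2 is tested with one common lens OR: `trta` and `parcat6` as main effects, without their interaction. A level at which all three lenses are at ceiling carries no information on the lens difference and can be left out of that fit.
2. Report the level-specific counts descriptively.
3. State that a non-converged or unbounded interval is not evidence of no difference.
4. Change `lens` to `trta` in the ESTIMATE statement; the printed effect name is not in the model. This is a code slip and does not bear on the ceiling question.

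A penalised fit that keeps the interaction, or an analysis of total correct out of 20, would also avoid the failure, but they differ in estimand or power, so one should be named in advance. In either case, confirm that counts are captured by contrast level: Protocol 2.2.2 says so, whereas step 2.11 of Visit 2 has the EDC record only total targets correct.

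The cost is SAP and code wording. When the fallback applies, level-specific lens effects become descriptive and a loss confined to the easiest level is detected less well.

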3.6.	Randomization	
Refer to pre-determined randomization order of testing (counter balancing) for the three test treatments. The final contact lens powers found in Visit 1 will be used.
 
 • Test contact lenses (worn with spectacle frame without lenses) • OASYS clear contact lenses (worn with spectacle frame without lenses) • OASYS clear contact lenses (worn with photochromic spectacles) 	
3.7.	Lens Insertion	
The Investigator or the subject inserts the study lenses. Record the time of lens insertion. Check for lens damage under the slit lamp before proceeding with lens settling. Replace damaged lenses if applicable.
	
3.8.	Lens Settling	
Allow the study lenses to settle for a minimum of 15 minutes.
 
Note: for nighttime testing, sufficient time is allowed for the subject to dark adapt.
	
3.9.	Pupillometry	
Measure the right eye pupil diameter during distance fixation (3 measures) using NeurOptics Pupillometer while subject seated in vehicle.
 
EDC: record pupil diameters in mm (0.1 mm increments)
	
3.10.	Illuminance levels	
Measurement of lighting level on the track outside the vehicle and at the plane of the eye in the vehicle.
 
 • For daytime testing, the illuminance must be > 1000 lux. • For nighttime testing, the illuminance must be < 10 lux. 
EDC: record outside and inside illuminance in lux rounded to the nearest whole number.
	

Visit 3: Closed-circuit on-road driving performance 1 (Day/night condition based on randomization)			
Step	Procedure	Details	
3.11.	Driving assessment	
Subject performs three laps of the circuit while under assessment. Measurements recorded include:
 
 1. Sign recognition 
 a. EDC: record % signs correctly identified b. EDC: record distance to signs in meters 2. Hazard avoidance 
 a. EDC: record % hazards hit 3. Driving time 
 a. EDC: record lap time in seconds b. EDC: record the % time in wrong lane 4. Pedestrian recognition distance 
 a. EDC: record distance to recognition in meters 
A composite driving Z score will be calculated afterwards using measures listed above.
	
3.12.	Subjective Questionnaire	Administer subjective questionnaire regarding driving task just completed. This will be a paper-administered questionnaire.	Appendix A

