Proportion of correctly identified signs and proportion of hazard avoidance will be analyzed separately using a generalized linear mixed model with beta distribution and logit link function. Each model will include sequence, period, lens type, first order carry-over, driving time (day or night), and the interactions lens type by driving time and period by driving time as fixed effect factors. An unstructured covariance matrix (UN) will be used to model the correlation between measurements from the same subject across periods.

The null and alternative hypotheses for no-difference between Test and Control 1 are as follows:

$$\begin{aligned} H_0: OR &= 1 \\ H_A: OR &\neq 1, \end{aligned}$$

where OR is the odds ratio of hazard avoidance at night driving time of Test over Control 1. No statistical difference between Test and Control 1 will be concluded if 1 falls within the 95% confidence interval of the odds ratio.

Pedestrian Distance Recognition and Road Sign Recognition

Pedestrian distance recognition and road sign recognition distance (or log-transformed distance) will be analyzed separately using a linear mixed model; sequence of lens wear, period, lens type, first order carry-over, driving time (day or night), and the interactions between lens type by driving time and period by driving time will be included in the model as

fixed effects. Age will be included as fixed covariate when appropriate. An appropriate covariance structure will be selected to model the correlation between measurements across periods within the same subject and driving time. Covariance structures that will be considered include:

- Compound Symmetry (CS)
- Heterogeneous Compound Symmetry (CSH)
- Unstructured (UN)
- Ante-dependence (ANTE(1))

For ANTE(1) structure, subject and driving time nested within subject will be included in the model as random effects. For the remaining structures, only subject will be included as random effect. The covariance structure that returns the lowest Akaike Information Criteria Corrected (AICC) will be selected as the structure that best fit the data¹¹. Heterogeneous residuals covariance structures (R-side) across driving time will be considered when appropriate. The log-likelihood ratio test will be used to test for the homogeneity between the residual covariance structures. The Kenward and Roger method will be used for the denominator degree of freedom.

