2.3. Data Handling Rules

Missing or spurious values will not be imputed as the number of missing values is expected to be low. The count of missing values will be included in the summary tables and listings. Dropout is expected to be one of the main reasons of missing data in the trial. Past soft contact lens trials don't provide any evidence that subject dropout is systematic or not at random.

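### The beta model for hazard avoidance and sign recognition has no rule for 0% or 100%, so a run with no hazard hit cannot enter the fit as written

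*SAP*

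**What the plan says.** Protocol 14.6 specifies the model: "Proportion of correctly identified signs and proportion of hazard avoidance will be analyzed separately using a generalized linear mixed model with beta distribution" and a logit link. SAP 6.2 keeps it, stating for signs and hazards alike that the "proportion of hazard avoidance will be analyzed separately using a generalized linear mixed model with beta distribution and logit link function". The code in SAP Appendix A fits the raw value of the endpoint with "DDFM=KR2 S DIST=BETA LINK=LOGIT". There is no events/trials form, no transformation and no inflation component.

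Hazard avoidance is scored out of nine foam hazards (SAP 5.1 and 6.1). Protocol 7.2, step 3.11, instructs "EDC: record % hazards hit", so a clean run is stored as 0% hit, which is 100% avoided. The same step says "Subject performs three laps of the circuit while under assessment" and does not say whether hazards are counted per lap or pooled. For signs, SAP 6.1 gives "typically about 42 signs dependent on the route travelled".

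The only fallback in SAP 6.2 for this model is from an unstructured to a compound-symmetry covariance. SAP 2.3 says "Missing or spurious values will not be imputed as the number of missing values is expected to be low", which does not address valid values of 0 or 100%.

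For the Landolt C counts, Appendix A uses a different form: "MODEL aval/n= age sexn tseqpg2 aperiod trta|parcat6 carry1a / S DIST=BINOMIAL LINK=LOGIT".

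**The concern.** Both endpoints are counts out of a known number, but the plan treats them as continuous proportions strictly between 0 and 1. The best possible result lies outside the support of the chosen distribution. The analyst must therefore drop clean runs or pick a boundary rule with the data in hand.

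Dropping them is not neutral. A better lens yields more clean runs and loses more of them, so a true difference shrinks and the sample gets smaller. SAP 6.2 concludes no statistical difference when the 95% confidence interval for the odds ratio includes 1, so both effects favour that conclusion. At stake are secondary hypotheses 3 and 5 (signs and hazards at night against Control 1) and the matching Control 2 comparisons in SAP 7.

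**Working it through.** **Inputs from the documents.** 9 hazards, about 42 signs, three laps per assessment (so 27 hazards if pooled), 24 completers, three lenses. That gives 24 × 3 = 72 night runs. The plan states no rate or power for these endpoints, so there is no figure to reproduce.

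**Assumption.** Avoidance probability p per hazard (or sign) is 0.60 to 0.95, with independent hazards.

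**1. Likelihood at the boundary.** The beta log-density with mean μ and precision φ is a constant + (μφ − 1) log y + ((1 − μ)φ − 1) log(1 − y). At y = 1 the last term is infinite. With μ = 0.80, φ = 10 its coefficient is 2 − 1 = 1, giving −∞. With μ = 0.95, φ = 10 it is 0.5 − 1 = −0.5, giving +∞. The binomial contribution at k = n is n log p, which is finite (9 × log 0.90 = −0.95).

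**2. How often a perfect run occurs:** pⁿ.

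| p | 9 hazards | 27 hazards | 42 signs |
|---|---|---|---|
| 0.60 | 1.0% | 0.0% | 0.0% |
| 0.70 | 4.0% | 0.0% | 0.0% |
| 0.80 | 13.4% | 0.2% | 0.0% |
| 0.90 | 38.7% | 5.8% | 1.2% |
| 0.95 | 63.0% | 25.0% | 11.6% |

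With 9 hazards, the expected number of clean runs among the 72 is 9.7 at p = 0.80, 27.9 at 0.90 and 45.4 at 0.95. A run with every hazard hit is negligible at p of 0.70 or more.

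**3. Odds ratio if perfect runs are dropped.** The mean of the remaining runs is (p − pⁿ)/(1 − pⁿ). For n = 9:
- p = 0.90: (0.9000 − 0.3874)/(1 − 0.3874) = 0.837
- p = 0.80: (0.8000 − 0.1342)/(1 − 0.1342) = 0.769

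The odds ratio becomes (0.769/0.231)/(0.837/0.163) = 0.65. The true value is (0.80/0.20)/(0.90/0.10) = 0.44. Subjects keeping both the Test and Control 1 night runs: 24 × 0.866 × 0.613 = about 13.

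| Test vs control | True OR | 9 hazards | 27 hazards | 42 signs |
|---|---|---|---|---|
| 0.60 vs 0.70 | 0.64 | 0.67 | – | – |
| 0.80 vs 0.90 | 0.44 | 0.65 | 0.47 | 0.45 |
| 0.90 vs 0.95 | 0.47 | 0.80 | 0.60 | 0.53 |

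**4. Simulation.** 1,000 trials per setting, night runs only, 24 subjects, three lenses in the Williams design, Test at the lower rate and both controls at the higher. Subject intercept SD was 0.6 on the logit scale (assumed), with lens and period effects and Wald tests at 5%. A beta mixed model on runs strictly inside (0, 1) was compared with a binomial mixed model on all runs.

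| Setting | OR: true → beta | Power: binomial → beta |
|---|---|---|
| 9 hazards, 0.60 vs 0.70 | 0.64 → 0.70 | 56% → 51% |
| 9 hazards, 0.70 vs 0.80 | 0.58 → 0.68 | 64% → 53% |
| 9 hazards, 0.80 vs 0.90 | 0.44 → 0.66 | 83% → 56% |
| 9 hazards, 0.85 vs 0.95 | 0.30 → 0.63 | 95% → 56% |
| 27 hazards, 0.80 vs 0.90 | 0.44 → 0.49 | unchanged |
| 27 hazards, 0.90 vs 0.95 | 0.47 → 0.60 | 95% → 83% |
| 42 signs, 0.80 vs 0.90 | 0.44 → 0.46 | unchanged |
| 42 signs, 0.90 vs 0.95 | 0.47 → 0.54 | 99% → 97% |

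Binomial median odds ratios were within 0.01 of the truth in these settings.

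**5. If a boundary rule is chosen later.** A common squeeze is (y(N − 1) + 0.5)/N. It moves a clean run to 0.944 with N = 9, 0.979 with N = 24 and 0.997 with N = 144 (logits 2.83, 3.85 and 5.66). I fitted a beta distribution to the expected squeezed scores (9 hazards, 0.80 vs 0.90, separate precision per lens). The odds ratios are 0.56, 0.50, 0.47 and 0.46 for N = 9, 24, 72 and 144, against a true 0.44. The answer depends on an N that the plan does not give.

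**The case against.** The gap in the text is not in dispute; the objections concern size, direction and remedy.

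- **Direction.** Omission is only one possible outcome. After a squeeze, the difference in mean logits (9 hazards, 0.80 vs 0.90) gives an odds ratio of about 0.31 with N = 72 or 0.26 with N = 144, which is away from 1. That is a moment shortcut. The beta model itself gives 0.46 to 0.56 on the same data, so this point does not stand.
- **Assumptions.** The rate, the subject SD and independence are all assumed. The shares in step 2 ignore subject variation; with SD 0.6 and 9 hazards they become 7.4% at 0.70 and 16.9% at 0.80. The simulation leaves out driving time, sequence, carry-over, R-side terms and the Kenward-Roger adjustment. With equal rates, dropping perfect runs leaves the odds ratio at 1. All of this stands: the power figures illustrate the effect and are not properties of the planned model.
- **Denominator.** The documents say nine, and 27 appears nowhere. True, but three laps with no pooling rule leave it open, and the effect depends on it.
- **SAP 2.3.** It covers missing or spurious values only. It neither supplies a boundary rule nor forbids one. That stands.
- **Remedy.** One pre-specified boundary rule would close the gap without changing the distribution. That is also true, but it is the weaker option when the SAP already has a model that needs no such rule.

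**Conclusion.** The concern holds. That 0% and 100% have no usable beta likelihood, and that neither document says what to do with them, follows from the text and the mathematics with high confidence. The size is less certain, because the avoidance rate and the denominator are not documented.

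Under the stated assumptions the effect is small at avoidance rates of 0.70 or below. It is material for 9 hazards at 0.80 to 0.95, smaller with 27 hazards, and small to modest for signs. It bears on detecting a true difference between lenses; no claim is made about type I error. The primary composite averages Z-scores in a linear mixed model and is untouched. Reading a confidence interval that includes 1 as no difference is a separate weakness, which this change does not cure. The point should be fixed before unmasking.

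**What to change.** Analyse hazards avoided out of n and signs correct out of n with the events/trials form already in Appendix A: binomial distribution, logit link, random subject effect, an R-side structure for overdispersion, and the fixed effects listed in SAP 6.2. State whether n is 9 or 27 hazards per assessment, and give the number of signs on each route. If the beta model is kept, the minimum is one boundary rule fixed in advance, including the N it uses, with a sensitivity analysis.

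The cost is one MODEL statement and two sentences, plus some data work. The EDC holds percentages and sign counts vary by route, so denominators must be fixed and merged in. SAP 6.1 also mentions about 65 items of information, so it should say that signs, not items, are counted.

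In the same edit, align the code with the text. SAP 6.2 lists sequence-by-time and carry-over-by-time interactions for these endpoints, and the Appendix A code omits them. SAP 6.2 lets non-significant interactions be removed, so the code may show a reduced model; if so, it should say so.
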